2.10 Patient-reported outcomes

Immune thrombocytopenia is associated with symptoms of fatigue, bruising, and bleeding, which can interfere with daily activities. Consequently, patients with ITP have decreased health-related quality of life (HRQoL) compared with healthy individuals. To assess patient-reported outcomes (PROs), HRQoL changes over time and association between HRQoL and platelet response during treatment with eltrombopag will be assessed using standard validated instruments in patients with ITP who are refractory to treatment or who relapsed after first-line steroids.

2.10.1 The Functional Assessment of Chronic Illness Therapy-Fatigue (FACIT-Fatigue) instrument is a 13-item, easy-to-administer, validated tool used to measure an individual's level of fatigue during usual daily activities over the past 7 days (Cella 2002, Webster 2003). FACIT-Fatigue is a subscale of the FACIT measurement system, which is a validated collection of HRQoL questionnaires targeted to the management of chronic illness that are used to measure HRQoL on multiple general and disease-specific domains. FACIT-fatigue is scored using a 4-point Likert scale. Items are scored as follows: 4=Not At All; 3=A Little Bit; 2=Slightly; 1=Quite A Bit; 0=Very Much, EXCEPT items #7 and #8 which are reversed scored. Score range from 0-52. A score of less than 30 indicates severe fatigue. The higher the score, the better the quality of life. Patients will be administered the FACIT-Fatigue at baseline, every 3 months during treatment, and end of treatment (EOT). A minimal clinically important difference from baseline in FACIT-Fatigue score will be evaluated (Cella 2002). The overall total score will be evaluated; [REDACTED]. Mean, SD, median, maximum, minimum, 25th and 75th percentile will be provided. Box plots at baseline, 3, 6, 9, 12, 15, 18, 21, 24 months and EOT will be provided. Descriptive statistics will be used to summarize change from baseline at month 3, 6, 9, 12, 15, 18, 21, 24 and EOT.

2.10.2 The Medical Outcome Trust's Short-Form 36 Health Survey, Version 2 (SF-36v2), which is a validated instrument used to measure general physical and mental health status

(Ware 2000), will be used to assess the impact of ITP on physical function and ability to conduct day-to-day activities. The SF-36v2 is used to measure patients' overall HRQoL via assessment of 8 domains—Physical Functioning, Role Physical, Bodily Pain, General Health, Vitality, Social Functioning, Role Emotional, and Mental Health. The SF-36 is scored using norm-based scoring procedures and scores ranging from 0-100; higher scores represent better HRQoL. Two summary scores, the Physical Component Score (PCS) and the Mental Component Summary (MCS), can also be calculated.

The SF-36v2, specifically the Physical Functioning and the Role Physical domains, demonstrated good reliability and validity for measuring the proposed constructs in the ITP population (Signorovitch 2011). The Physical Functioning domain includes 10 items related to limitations in physical functioning and is scored using a 3-level Likert scale (1=yes, limited a lot; 2=yes, limited a little; and 3=no, not at all limited); higher scores represent less functional limitation. The Role Physical domain is used to measure to what degree physical health interferes with work/other daily activities, includes 4 items (reduction in the amount of time spent on work/other activities, accomplishing less than one would like, limitations in kind of work/other activities, and difficulty performing work/other activities), and is scored using a 5-level Likert scale (1=all of the time; 5=none of the time); lower scores represent less impact on daily activities. Patients will be administered the SF-36v2 at baseline, every 3 months during treatment, and EOT, and change from baseline will be evaluated. [REDACTED]

[figure not shown]
[REDACTED] Mean, SD, median, maximum, minimum, 25th and 75th percentile will be provided. Box plot at baseline, 3, 6, 9, 12, 15, 18, 21, 24 months and EOT will be provided. Descriptive statistics will be used to summarize change from baseline at month 3, 6, 9, 12, 15, 18, 21, 24 and EOT.

2.10.3 Functional Assessment of Cancer Therapy - Thrombocytopenia 6-item version (FACT-Th6) instrument is used to measure worry/concern about bleeding and bruising, and the impact of this worry/concern on physical and social activity (Cella 2006). FACT-Th6 is a 6-item subset of the more detailed FACT-Th, which is an 18-item subscale of the validated FACT that specifically measures concerns related to thrombocytopenia in the past 7 days. The FACT-Th6 is scored using a 5-level Likert scale (0=not at all to 4=very much) and is calculated by summing scores for the 6-items; therefore, scores can range from 0–24, with higher scores representing better HRQoL. No minimum clinically important change thresholds have been established for FACT-Th6. Tentatively anchor-based methods (e.g., based on Patient Global Impression of Change [PGIC] and Patient Global Impression-Severity [PGIS]) and distribution-based methods will be used to determine meaningful change in scores. FACT-Th6 demonstrated good reliability and validity for measuring the proposed constructs in the ITP population. Patients will be administered the FACT-Th6 at baseline, every 3 months during treatment, and EOT. Mean, SD, median, maximum, minimum, 25th and 75th percentile will be provided. Box plot at baseline, 3, 6, 9, 12, 15, 18, 21, 24 months and EOT will be provided. Descriptive statistics will be used to summarize change from baseline at month 3, 6, 9, 12, 15, 18, 21, 24 and EOT.

2.10.4 GP5, which is a single question, is used to assess the overall bothersomeness of treatment side effects. The GP5 is scored using a 5-point rating scale (0 = not at all; 1 = a little bit; 2 = somewhat; 3 = quite a bit; and 4 = very much), where lower scores reflect less bothersomeness from treatment side effects. The GP5 will be evaluated at baseline, 12 months, 24 months and EOT. The frequencies and percentages for each of the rating points will be provided.

Descriptive statistics will be used to summarize change from baseline to >0-3 months, >3-6 months, >6-9 months >9-12 months, >12 months and EOT. Shift table from baseline to worst post-baseline value will also be provided.

2.10.5 Treatment Satisfaction Questionnaire for Medication (TSQM-9) will be used to assess treatment satisfaction with medication. The three scales of the TSQM-9 include the effectiveness scale, convenience scale, and global satisfaction scale. TSQM-9 will be evaluated at baseline, month 12, month 24 and EOT. Mean, SD, median, maximum, minimum, 25th and 75th percentile will be provided at the time points. Descriptive statistics will be used to summarize change from baseline at month 12, month 24 and EOT. Shift table from baseline to worst post-baseline value will also be provided.

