5.2 Exclusion criteria

Patients meeting **any** of the following criteria are not eligible for inclusion in this study.

1. ITP patients previously treated with any ITP second-line therapies, TPO-RA for ITP, except steroids / IVIG as described in the inclusion criteria
2. Patients who relapsed more than one year after the end of first-line full course of steroid therapy
3. Patients with a diagnosis of secondary thrombocytopenia.
4. Patients who are unable to participate in assessments/biological studies
5. Patients who have life threatening bleeding complications per investigator discretion
6. Patients who had a deep vein thrombosis or arterial thrombosis in the 6 months preceding enrollment
7. Presence of moderate to severe impaired renal function as indicated by any or all of the following criteria:
 - Creatinine clearance $< 45 \text{ mL/min}$ as calculated using Cockcroft-Gault formula
 - Serum creatinine $> 1.5 \text{ mg/dL}$
8. Total bilirubin $> 1.5 \times$ upper limit of normal (ULN)
9. Aspartate transaminase (AST) $> 3.0 \times$ ULN
10. Alanine transaminase (ALT) $> 3.0 \times$ ULN
11. Patients who are human immune deficiency virus (HIV), hepatitis C virus (HCV) or hepatitis B surface antigen (HBsAg) positive. These assessments can be performed using the local laboratory used by the site. Central laboratory testing is available for HIV, HCV, and HBsAg should local laboratory testing not be available.
12. Patients with hepatic impairment (Child-Pugh score > 5)
13. Patients who are unable to respect the 4-hour interval between eltrombopag and other medications (e.g., antacids), calcium-rich foods (e.g., dairy products and calcium fortified juices), or supplements containing polyvalent cations such as iron, calcium, aluminum, magnesium, selenium, and zinc
14. Patients who are unable to stop medications that are known to cause a drug-drug interaction with eltrombopag
15. Patients who have active malignancy
16. Patients with any serious and/or unstable pre-existing medical, psychiatric disorder or other conditions that could interfere with patient's safety, obtaining informed consent or compliance with the study procedures as per investigator discretion
17. Patients with a known immediate or delayed hypersensitivity reaction or idiosyncrasy to eltrombopag or drugs chemically related to eltrombopag or excipients that contraindicate their participation

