Patients should be seen for all visits/assessments as outlined in the assessment schedule or as close to the designated day/time as possible. Missed or rescheduled visits should not lead to automatic discontinuation. Patients who prematurely discontinue the study for any reason should be scheduled for a visit as soon as possible, at which time all of the assessments listed for the final visit will be performed. At this final visit, all dispensed eltrombopag study treatment supplies should be reconciled, and the adverse event and concomitant medications recorded on the CRF.

Table 8-1 Assessment schedule

Screening to Week 9

Period	Screening	Treatment									
		Week 1 Day 1	Week 2 Day 1	Week 3 Day 1	Week 4 Day 1	Week 5 Day 1	Week 6 Day 1	Week 7 Day 1	Week 8 Day 1	Week 9 Day 1	
Visit Name	Screening										
Visit Number	1	110	120	130	140	150	160	170	180	190	
IRT											
IRT registration	X										
IRT enrollment		X									

X = assessment to be recorded in the clinical database or received electronically from a vendor
S = assessment to be recorded in the source documentation only
a= Should be administered before IP administration
**= on monthly basis or as per local standard, if no visit planned the test can be performed at home with urine pregnancy test. Only blood test results will be collected in the eCRF)

Weeks 11 to follow-up

Period	Treatment																				End of Treatment	Safety Follow-up	
	Week 11 Day 1	Week 13 Day 1	Week 15 Day 1	Week 17 Day 1	Week 19 Day 1	Week 21 Day 1	Week 23 Day 1	Week 25 Day 1	Week 27 Day 1	Week 29 Day 1	Week 31 Day 1	Week 33 Day 1	Week 35 Day 1	Week 37 Day 1	Week 39 Day 1	Week 41 Day 1	Week 43 Day 1	Week 45 Day 1	Week 47 Day 1	Week 49 Day 1	Week 51 Day 1		
Visit Name	200	210	220	230	240	250	260	270	280	290	300	310	320	330	340	350	360	370	380	390	400	1999	SFUP
Visit Number																							
IRT enrollment																						X	

X = assessment to be recorded in the clinical database or received electronically from a vendor
S = assessment to be recorded in the source documentation only

* Patients who have achieved sustained remission at month 12 will be followed quarterly for an additional 12 months to obtain further data on response and remission duration.

** On monthly basis or as per local standard, if no visit planned the test can be performed at home with urine pregnancy. Only blood test results will be collected in the eCRF)

Follow-up Period for Responders

Period	Treatment				Safety Follow-up

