Th12	I am frustrated by not being able to do my usual activities ..	0	1	2	3	4

Table 16-7 FACT-G (Version 4)Please circle or mark one number per line to indicate your response as it applies to the past 7 days.

PHYSICAL WELL-BEING		Not at all	A little bit	Some-what	Quite a bit	Very much
GP1	I have a lack of energy	0	1	2	3	4
GP2	I have nausea	0	1	2	3	4
GP3	Because of my physical condition, I have trouble meeting the needs of my family	0	1	2	3	4
GP4	I have pain	0	1	2	3	4
GP5	I am bothered by side effects of treatment	0	1	2	3	4
GP6	I feel ill	0	1	2	3	4
GP7	I am forced to spend time in bed	0	1	2	3	4
SOCIAL/FAMILY WELL-BEING		Not at all	A little bit	Some-what	Quite a bit	Very much
GS1	I feel close to my friends	0	1	2	3	4
GS2	I get emotional support from my family	0	1	2	3	4
GS3	I get support from my friends	0	1	2	3	4
GS4	My family has accepted my illness	0	1	2	3	4
GS5	I am satisfied with family communication about my illness	0	1	2	3	4
GS6	I feel close to my partner (or the person who is my main support)	0	1	2	3	4
Q1	Regardless of your current level of sexual activity, please answer the following question. If you prefer not to answer it, please mark this box  and go to the next section.					
GS7	I am satisfied with my sex life	0	1	2	3	4

Table 16-8 Treatment Satisfaction Questionnaire (TSQM)**Instructions:**

Please take some time to think about your level of satisfaction or dissatisfaction with the medication you are taking. We are interested in your evaluation of the effectiveness, side effects, and convenience of the medication *over the last two to three weeks, or since you last used it*.

For each question, please place a single check mark below the response that most closely corresponds to your own experiences.

1. How satisfied or dissatisfied are you with the ability of the medication to prevent or treat your condition?

Extremely Dissatisfied	Very Dissatisfied	Dissatisfied	Somewhat Satisfied	Satisfied	Very Satisfied	Extremely Satisfied
						
 1	 2	 3	 4	 5	 6	 7

2. How satisfied or dissatisfied are you with the way the medication relieves your symptoms?

Extremely Dissatisfied	Very Dissatisfied	Dissatisfied	Somewhat Satisfied	Satisfied	Very Satisfied	Extremely Satisfied
						

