$PDI \text{ (dosing unit / unit of time)} = \text{Planned cumulative dose (dosing unit)} / \text{Duration of exposure (unit of time)}$.

Note that eltrombopag is administered with a tapering regime. Therefore, for some patients, the duration of exposure will not include the time after tapering when they are not getting any dose. The **planned dose** is the starting dose of treatment which was defined for the patient by protocol.

Relative dose intensity (RDI) is defined as follows:

RDI = DI (*dosing unit / unit of time*) / PDI (*dosing unit / unit of time*).

e.g. RDI = DI (92.7 mg/day) / PDI (100 mg/day) = 0.927

Study day

The study day for efficacy (platelet counts) and safety assessments (e.g. adverse event onset, laboratory abnormality occurrence, vital sign measurement, dose interruption etc.) will be calculated as the difference between the date of the event (onset date of an event, assessment date etc.) and the start of study treatment plus 1. The first day of study treatment is therefore study day 1. Example: if start of study treatment is on 05-Jan-2014 and start date of an adverse event is on 09-Jan-2014 then the study day of the adverse event onset is 5. For safety assessments before start of study treatment, the study day is negative and derived by (date of event – start date of study treatment). For example: if start of study treatment is on 05-Jan-2014 and date of lab measurement is on 02-Jan-2014 then the study day of the laboratory abnormality is -3. Note, the day of start of study treatment is day 1, and the day before the date of first study treatment is day – 1, not day 0.

Baseline

The **baseline** is the result of an investigation describing the “true” state of the patient before start of eltrombopag.

The last available assessment on or before the date of start of eltrombopag is taken as “baseline” assessment. In case, assessment is captured pre-dose on first day of eltrombopag (e.g. PROs), this assessment is used for baseline.

On-treatment assessments and observation periods

The overall observation period will be divided into three mutually exclusive segments:

1. **pre-treatment period:** from day of patient’s informed consent to the day before first dose of eltrombopag

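### GP5 and TSQM-9 are not split by whether patients are on or off eltrombopag, so the pooled GP5 results cannot be read as the drug's side-effect burden

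*SAP*

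**What the plan says.** Objectives 8 and 9 (Protocol Table 2-1, SAP Table 1-1) explore side-effect impact with GP5 and treatment satisfaction with TSQM-9. The endpoint for each is the overall change from baseline to month 12 and end of treatment (EOT).

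- **Instruments (Protocol Appendix 3).** GP5 asks for agreement with "I am bothered by side effects of treatment", with a 7-day recall. TSQM-9 asks the patient to "think about your level of satisfaction or dissatisfaction with the medication you are taking". Its recall is two to three weeks, with the alternative of going back to the last use.
- **Baseline (SAP 2.1.1).** "In case, assessment is captured pre-dose on first day of eltrombopag (e.g. PROs), this assessment is used for baseline". A footnote to Protocol Table 8-1 agrees: "a= Should be administered before IP administration". Exclusion criterion 1 in Protocol 5.2 rules out "ITP patients previously treated with any ITP second-line therapies, TPO-RA for ITP, except steroids / IVIG as described in the inclusion criteria".
- **Timing.** SAP 2.10.4: "The GP5 will be evaluated at baseline, 12 months, 24 months and EOT". SAP 2.10.5 gives the same times for TSQM-9. Protocol 8.5.1 gives only baseline and end of treatment, and the follow-up part of Table 8-1 lists both instruments only at month 24.
- **Analysis.** For GP5, SAP 2.10.4 plans rating frequencies, a shift table to the worst post-baseline value, and this: "Descriptive statistics will be used to summarize change from baseline to >0-3 months, >3-6 months, >6-9 months >9-12 months, >12 months and EOT". For TSQM-9, SAP 2.10.5 plans summary statistics at each time point, a shift table, and this: "Descriptive statistics will be used to summarize change from baseline at month 12, month 24 and EOT".
- **Splits.** SAP 2.7.2 item 7 reports FACIT-Fatigue, FACT-Th6 and SF-36v2 by month-12 SRoT status. Items 8 and 9 (GP5 and TSQM-9) and Sections 2.10.4 and 2.10.5 state no split. SAP 2.2.1 promises a split by SRoT status for selected outputs without naming these two.

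**The concern.** Both instruments ask about treatment, but which treatment is being rated changes between time points and between patients. At baseline nobody has taken eltrombopag. At month 12 some patients are taking it and others have stopped, in many cases long before. At month 24 most of those left should be off it. A pooled change therefore subtracts a pre-eltrombopag reference from a mixture of on-drug and off-drug answers, and pooled GP5 frequencies mix the same answers.

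The stake is how objective 8 is interpreted, and to a lesser degree objective 9. If a pooled GP5 table is reported as patients' experience of eltrombopag side effects, the figure depends partly on how many patients had stopped the drug, which is an efficacy result and not a tolerability result.

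**Working it through.** Neither document gives the number of on-drug and off-drug answers, so there is no stated figure on this point to reproduce. The 25% rate is the planning rate in SAP 3.1.1. The design figures for 105 patients in SAP 3.1.2 do reproduce: a cut-off of 23 gives alpha 0.0373 and power 0.7995, against 0.037 and 0.800 stated.

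**1. What each time point measures**

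- *Baseline:* pre-dose, with no earlier TPO-RA. The answer concerns steroids with or without IVIG, or no current drug. Exclusion criterion 2 bars only relapse more than one year after the end of first-line steroids, so some patients may be months past steroids.
- *Month 12, responders:* SAP 2.5.1 requires taper to discontinuation and then maintenance to month 12. They are off drug.
- *Month 12, others:* Protocol Table 6-1 keeps patients who have not reached the target count on drug to month 12, and Section 9.2 has drug stop at the Week 53 visit. These patients answer on drug.
- *Month 24:* only month-12 responders enter follow-up (Protocol 6.1.3 and 9.3). They are off drug unless re-treated after relapse.
- *EOT:* SAP 2.7.3 takes the last assessment whatever its timing, so for patients in follow-up it falls in follow-up. SAP 2.1.1 admits the end-of-treatment assessment only within 30 days of last treatment. The two rules are not reconciled for responders.

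**2. Off-drug responders at month 12**

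Inputs: N = 105 (SAP 3.1.2) and SRoT rate s = 0.25 (SAP 3.1.1). The early discontinuation rate d = 0 to 0.30 is an assumption, and all other assessed non-responders are taken to be on drug.

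- Off-drug responders: 0.25 × 105 = 26.25, about 26. Non-responders: about 79.
- Share of those assessed, s / (1 − d): 0.25 / 1.00 = 25%, to 0.25 / 0.70 = 36%.
- On drug at month 12, 105 × (1 − s − d): 105 × 0.75 = about 79, to 105 × 0.45 = about 47.
- At the null rate of 15%: 0.15 × 105 = about 16 responders, and a share of 15% to 0.15 / 0.70 = 21%.

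**3. Time off drug against the recall period**

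Two months is 2 × 30.4375 / 7 = 8.7 weeks. With 25 mg steps every two weeks and a final alternate-day step, the taper takes 4 weeks from 50 mg or 6 weeks from 75 mg. The week of complete response is an assumption.

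- Response at week 1, 4-week taper: off drug at 1 + 8.7 + 4 = 13.7 weeks, so 52 − 13.7 = 38.3 weeks off by week 52.
- Response at week 8, 6-week taper: off drug at 8 + 8.7 + 6 = 22.7 weeks, so 29.3 weeks off.

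Early responders are therefore roughly 29–38 weeks off drug, far beyond the 7-day GP5 recall. A later response or repeated attempt shortens this.

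**4. Effect on a pooled level**

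If the off-drug mean differs from the on-drug mean by D, the pooled mean differs from the on-drug mean by share × D, that is 0.25 × D to 0.36 × D. The documents give neither the size nor the sign of D.

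**The case against.** The strongest reply has several parts.

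- **Most patients are not responders.** At the planned rate about 79 of 105 are not, and those still treated at Week 53 answer while on eltrombopag. Their change from baseline is confounded by earlier therapy but informative. A reader might infer that the planned change does not measure eltrombopag at all. The documents do not support that.
- **The direction of bias is unknown.** A reader might infer that fading steroid effects and stopped drug make the result favour eltrombopag. Patients already well past steroids at baseline could have little to report, and their change could look unfavourable. The mix is not given.
- **TSQM-9 differs from GP5.** Its instruction lets a patient off drug rate the medication last used, so off-drug answers may still concern eltrombopag.
- **Levels are already planned, and table layouts sit in shells outside these documents.** A split by SRoT status under SAP 2.2.1 is not excluded.
- **The schedule is not fully visible.** The year-1 PRO rows of Table 8-1 cannot be read in the text reviewed, and the GP5 change windows before month 12 suggest some earlier answers, perhaps only from early EOT visits. On-treatment visits cannot be ruled out, although Protocol 8.5.1 lists none.
- **The endpoint is the protocol's own.** In a trial of tapering to stop, burden at month 12 regardless of drug status is a legitimate description of the strategy.

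These points limit the claim but do not remove it. The planned levels have no stated split either. A split by SRoT status would be only a partial remedy: SAP 2.7.2 item 1c notes that month-12 responders are a subset of those who tapered off, so a tapered patient who then fails on a bleeding event can be a non-responder who is off drug. A strategy-level summary is defensible if labelled as such, but it does not show eltrombopag's side-effect burden.

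**Conclusion.** The point holds in limited form. As written, the SAP pools on-drug and off-drug answers for GP5 and TSQM-9 against a baseline that precedes any eltrombopag. At month 12 about 26 of 105 patients are off-drug responders at the planned 25% rate, or 25–36% of those assessed. This rests on assumed early discontinuation of 0–30% and on all other assessed patients being on drug. At month 24 all remaining patients are off drug unless re-treated.

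Pooled GP5 frequencies and changes therefore cannot be read as eltrombopag's side-effect burden. For TSQM-9 the off-drug problem is weaker because of its recall wording, but the baseline problem is the same. No direction of bias is claimed, nor that the instruments are uninformative. Both objectives are descriptive and untested, so the consequence is a risk of misreading, not an error in the trial's main inference.

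**What to change.** In SAP 2.10.4 and 2.10.5, and by reference in 2.7.2 items 8 and 9:

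- Present levels, changes and shift tables at month 12, month 24 and EOT by eltrombopag status at the assessment, derived from the dose record. For GP5, on drug means any non-zero dose in the previous 7 days. For TSQM-9, use on or off drug at the assessment, with a note that off-drug answers may refer to past eltrombopag.
- Base the eltrombopag conclusion for objective 8 on the on-drug GP5 levels.
- Label change from baseline as a contrast with the pre-eltrombopag state, for both instruments.

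The shift tables can stay if they are split. The change needs no new data: one derived flag and some SAP wording. SAP Section 1 says the primary CSR is already final, so the split month-12 tables would go into the final CSR. The cost is smaller groups in descriptive tables, with roughly 26 off-drug responders and 47–79 on-drug patients at month 12 under the assumptions above.
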